5.3.4. Corticosteroids

Subjects may receive topical, inhaled, enteric, or systemic corticosteroids while on study.

5.3.5. Granulocyte Colony-Stimulating Factors and Erythropoietin

Granulocyte-macrophage colony-stimulating factor (GM-CSF) should not be administered given the potential for GM-CSF-related inflammatory symptoms.

G-CSF (filgrastim, PEG-filgrastim, lenograstim) may be administered in response to Grade 4 neutropenia or neutropenic complications; (see [Table 5-2](#)).

While erythropoietic agents (eg, erythropoietin or darbepoetin) may be administered for Grade ≥ 3 anemia, their use in this study is discouraged given the potential to confound assessments of improvements in bone marrow function related to idelalisib.

5.3.6. Drugs that Alter CYP3A-Dependent Metabolism

Idelalisib is metabolized to its major metabolite [PPD](#) via aldehyde oxidase and cytochrome P450 3A (CYP3A). Idelalisib also undergoes minor metabolism by UDP glucuronosyltransferase 1-4 (UGT1A4). The AUC of idelalisib was increased 1.8 fold when idelalisib was coadministered with a strong CYP3A inhibitor. Therefore, if subjects are taking concomitant strong CYP3A inhibitors, the subject should be monitored closely for signs of idelalisib toxicity and the dose modifications for adverse reactions should be followed in the event of toxicity (see [Table 5-2](#)).

Additionally, idelalisib exposures are approximately 75% lower when coadministered with rifampin, a highly potent inducer of CYP3A. Therefore, avoid coadministration of strong inducers of CYP3A (rifampin, carbamazepine, phenytoin, and St. John's wort) with idelalisib.

5.3.7. Drugs that undergo CYP3A-Dependent Metabolism

The major metabolite of idelalisib, PPD is a reversible and time dependent inhibitor of CYP3A; accordingly, coadministration of idelalisib with midazolam, a probe CYP3A substrate, resulted in a ~5-fold increase in midazolam systemic exposure (AUC). Coadministration of drugs that are narrow therapeutic index CYP3A substrates with idelalisib may result in an increase in their systemic exposures (eg, antiarrhythmics, calcium channel blockers, benzodiazepines, certain HMG-CoA reductase inhibitors, phosphodiesterase-5 [PDE5] inhibitors, warfarin). Avoid coadministration of drugs that are narrow therapeutic index CYP3A substrates (eg, alfentanil, cyclosporine, sirolimus, tacrolimus, cisapride, pimozide, fentanyl, quinidine, ergotamine, dihydroergotamine, astemizole, terfenadine) with idelalisib.

5.3.8. Immunization

Because of its actions to inhibit PI3K δ -dependent B-cell function, high doses of idelalisib can impair primary or secondary responses to immunization in animals.

The specific clinical relevance of these findings with idelalisib is unknown. However, for subjects who are at substantial risk of an infection (eg, influenza) that might be prevented by immunization, consideration should be given to providing the vaccine prior to initiation of study therapy.

Of note, the safety of immunization with live viral vaccines following idelalisib therapy has not been studied and vaccination with live virus vaccines during study treatment is not recommended.

5.3.9. Ultraviolet Exposure

While nonclinical findings suggest the hypothetical potential for phototoxicity in humans, available clinical data do not reveal a photosafety concern. Although specific clinical correlates for these nonclinical data are not available, investigators and study subjects should be observant for the possibility that study participants may have exaggerated sunburn reactions (eg, burning, erythema, exudation, vesicles, blistering, edema) involving areas of skin exposed to ultraviolet light.

5.3.10. Surgery

There are no known effects of idelalisib on coagulation or wound healing. Pending receipt of additional information and considering the subject's current platelet counts, idelalisib may be continued in the peri-procedural period in subjects who require surgery or invasive procedures.

5.4. Accountability for Idelalisib

The disposition of all idelalisib should be documented from the time of receipt at the site through subject dispensing and return.

Study personnel must ensure that idelalisib is kept in a secure locked area with access limited to authorized personnel. The idelalisib must not be used outside the context of this protocol. Under no circumstances should the investigator or site personnel supply idelalisib to other investigators or clinics, or allow the idelalisib to be used other than as directed by this protocol.

The investigator and/or the responsible site personnel must maintain accurate records of the receipt of idelalisib shipped by Gilead Sciences or its designee, including, but not limited to, the date received, lot number, amount received, and the disposition of all idelalisib. Upon receipt of a drug shipment, the shipment must be logged into the idelalisib accountability records, these records must also be maintained to include the subject number to whom the idelalisib was dispensed and the date, quantity and lot number of the idelalisib dispensed.

Depending upon the decision of Gilead Sciences, remaining unused idelalisib supply will be returned to Gilead Sciences or its designee after the study is completed or will be discarded or destroyed at the clinical site. If the idelalisib is discarded or destroyed at the clinical site, standard institutional policy should be followed. Records documenting the date of idelalisib shipping or destruction, relevant lot numbers, and amount shipped or destroyed should be maintained.

5.4.1. Overdose Precautions

In Phase 1 studies, an MTD for idelalisib was not reached when administering the drug continuously at dose levels of 350 mg/dose BID (700 mg per day) {[Coutre et al 2011, Kahl et al 2011](#)}. However, in this protocol, an overdose is defined as administration of more than the prescribed daily dose (ie, >300 mg in a single day).

The Gilead Sciences medical monitor should be contacted if an idelalisib overdose occurs. Cases of idelalisib overdose will result in specific reporting requirements.

5.4.2. Inadvertent Exposure and Spill Precautions

Based on available data from nonclinical studies, idelalisib does not appear to be acutely toxic, genotoxic, or irritative at levels that are likely to result from inadvertent exposure to the contents of broken tablets. However, personnel handling the drug should use reasonable precautions to avoid eye contact, skin contact, inhalation, or ingestion of the idelalisib product. For further information regarding inadvertent exposure and spill precautions, please consult the idelalisib investigator brochure.

5.4.3. Investigational Medicinal Product Return or Disposal

Subjects will be instructed to return any unused idelalisib in the original container at post treatment study visits. Returned medication will be reconciled by the investigator in order to monitor the subject's compliance with the medication regimen. When possible, all idelalisib returned by the subject should be retained for review by the study site monitor prior to return to Gilead Sciences or destruction.

5.5. Discontinuation from Study

Subject study participation may be ended due to any of the follow reasons:

- Withdrawal of consent
- Objective evidence of disease progression.
- Unacceptable toxicity or unable to tolerate a second rechallenge for the same AE.
- Any subject who becomes pregnant or begins breastfeeding.
- Initiation of non-protocol specified anticancer therapy.
- Noncompliance with idelalisib administration, study procedures, or study requirements.
- The investigator may discontinue idelalisib, if it is not in the subject's best interest to continue.
- Any subject who is lost to follow-up.
- Death
- Discontinuation of study by the Sponsor, a regulatory agency, or an EC
- Any subject who is diagnosed with any grade SJS or TEN, Grade ≥ 2 pneumonitis, or any grade PJP.
- Any subject whose benefit-risk profile is not deemed positive by the investigator should discontinue study drug.

6. STUDY PROCEDURES

The study procedures to be conducted for each subject enrolled in the study are presented in tabular form in [Table 6-1](#) and described in the text that follows.

The investigator must document any deviation from protocol procedures and notify the sponsor or contract research organization (CRO).

6.1. Subject Enrollment

6.1.1. Subject Recruitment

This study will enroll subjects receiving GS-9820 in Study GS-US-315-0102 at the time of study closure who have had objective evidence of clinical benefit defined as at least stable disease on imaging assessed by the IRC and no toxicities prior to enrollment in this study that would preclude initiating therapy with idelalisib. The study sponsor will post a description of the study on the ClinicalTrials.gov website.

6.1.2. Subject Compensation for Participation

Subjects will not be paid for participation in the study other than medical care that may be provided. Payments for such items as lost wages, disability, discomfort due to injury, or meals obtained while waiting at the clinical research center will not be provided. Through the informed consent process, study candidates will be notified that their insurance company could be charged for standard care that is a component of this research study and that subjects may be responsible for co-payments and deductible payments that are typical for their insurance coverage.

6.1.3. Screening Visit

The investigator must inform each prospective subject of the nature of the study, explain the potential risks, and obtain written informed consent from the subject and/or a legal guardian prior to performing any study-related screening procedures.

From the time of obtaining informed consent through the first administration of investigational medicinal product, record all serious adverse events (SAEs), as well as any adverse events related to protocol-mandated procedures on the adverse events case report form (CRF/eCRF). All other untoward medical occurrences observed during the screening period, including exacerbation or changes in medical history are to be captured on the medical history CRF/eCRF. See [Section 7 Adverse Events and Toxicity Management](#) for additional details.

6.2. Treatment Assessments

From the time of obtaining informed consent through the first administration of investigational medicinal product, record all SAEs, as well as any non-serious all grade AEs on the AE case report form (eCRF). All other untoward medical occurrences observed during the screening

period, including exacerbation or changes in pre-existing conditions are considered medical history (not collected for this study). See Adverse Events and Toxicity Management (Section 7) for additional details.

While on study, the subject will return at regular intervals for the following procedures:

- Evaluation of disease status per standard of care
- Laboratory lab tests as outlined under section 6.2.2.
- Recording of all grade AEs and all SAEs
 - For an AE of Diarrhea or Colitis:
 1. Obtain history of onset and duration of diarrhea, including description of number of stools and stool composition (eg, watery, bloody, nocturnal), travel history, dietary changes and a medication review to identify possible diarrheogenic agents
 2. Perform physical examination including assessment for fever, dizziness, abdominal pain/cramping, and weakness (ie, evaluate for sepsis, bowel obstruction, dehydration)
- Return of used drug supplies and dispensing of new idelalisib supply

The specific study procedures to be conducted for each subject enrolled in the study are presented in Table 7-1 and are described in the sections that follow.

6.2.1. Clinical Evaluation

While on study, the subject will be followed for disease status according to standard of care. At each study visit the subject's disease status will be assessed. If no change in disease status is identified and the subject is dispensed additional idelalisib, the most recent prior response documented for the study will be recorded.

6.2.2. Laboratory Assessments

Blood samples for ALT, AST, total bilirubin will be collected at Screening, Day 1, Weeks 4, 8, 12, 16, 168, every 12 weeks thereafter, and the End of Study (EOS) Visit.

Blood samples for CMV will be collected at Screening and every 4 weeks thereafter throughout study participation.

Blood samples for ANC will be collected at Screening and every 2 weeks through Week 24.

Blood samples for Pneumococcal, Haemophilus Influenzae Type B (Hib), and Tetanus titers will be taken at screening

Blood samples for immune-monitoring will be collected at Screening, Weeks 4, 12 and every 12 weeks thereafter, and the EOS Visit:

- Lymphocyte subset panel using flow cytometry (immunophenotyping)
- Quantitative immunoglobulins: IgG, IgM, IgA
- Serum CH50 level

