5.2.5. Dispensing

The clinic staff (eg, pharmacist or other qualified person) will be responsible for dispensing idelalisib. It is planned that idelalisib will be dispensed at 4-week intervals through the first 16 weeks of treatment, at 8-weeks, and at 12-week intervals thereafter. Sufficient idelalisib will be provided for each study period at the beginning of the period. Tablets should be dispensed in the original bottles provided.

The clinic staff (eg, pharmacist or other qualified person) will write the subject number on each bottle that is dispensed. Immediately before dispensing, the clinic staff will write the bottle number for each dispensed bottle in the idelalisib administration record corresponding to the subject number.

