6.3. End of Study

Subjects will be withdrawn from this study if they develop progressive disease, unacceptable toxicity related to idelalisib, withdraw consent, are noncompliant, or are lost to follow up or die. In this event, the following procedures should be performed:

- Return of used and unused drug supply
- Recording of all Grade AEs and all SAEs
- Investigator Response Assessment
- Laboratory assessments as outlined in [Table 6-1](#)
- Recording of the reason for withdrawal
- Deaths occurring within 30 days following the last dose of idelalisib, even if occurring after the End of Study Visit, will be captured.

Table 6-1. Schedule of Study Procedures

Period	Screen	Treatment														End of study	
Visit	1	2	3	4	5	6	7	8	9	10	11	12	13	14	15+		End of study
Week	-4	0	2	4	6	8	10	12	14	16	18	20	22	24	Q4 weeks	Q12 weeks	End of study
Study Day	Within -28 days	1	14	28	42	52	70	84	98	112	126	140	154	168			End of study
Visit Window			±2	±2	±2	±2	±2	±2	±2	±2	±2	±2	±2	±2	±7	±7	
Informed consent	X																
Serum β-HCG ^a	X																
Pneumococcal, Hib, Tetanus titers	X																
ALT/AST/total bilirubin	X	X		X		X		X		X				X		X	
Urine pregnancy test ^a		X		X		X		X		X				X		X	
ANC ^b	X	X	X	X	X	X	X	X	X	X	X	X	X				
CMV surveillance	X			X		X		X		X		X		X	X ^c		
Immune Monitoring	X			X				X						X		X	
Assess adverse events and SAEs ^d		X		X		X		X		X				X		X	
Record concomitant medications ^e		X		X		X		X		X				X		X	
Idelalisib dispensing/accounting		X		X		X		X		X				X		X	
Investigator response assessment ^f	X			X		X		X		X				X		X	

Abbreviations: β-HCG=beta human chorionic gonadotropin, ALT=alanine aminotransferase, AST=aspartate aminotransferase, Hib = Haemophilus Influenzae Type B

a For women of child bearing potential; Serum β-HCG to be collected at screening, urine pregnancy test to be collected at visits from first dose of idelalisib to EOS

b Absolute neutrophil count (ANC) will be monitored at least every two weeks for the first 24 weeks of idelalisib treatment

c CMV surveillance must be conducted approximately every 4 weeks throughout the course of idelalisib treatment

d For an AE of Diarrhea/Colitis: 1) Obtain history of onset and duration of diarrhea, including description of number of stools and stool composition, travel history, dietary changes and a medication review to identify possible diarrheogenic agents and 2) Perform physical examination including assessment for fever, dizziness, abdominal pain/cramping, and weakness

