7.2.2. Assessment of Severity

The severity of AEs will be graded using the CTCAE, Version 4.03 and available at:
http://evs.nci.nih.gov/ftp1/CTCAE/CTCAE_4.03_2010-06-14_QuickReference_8.5x11.pdf

If a CTCAE criterion does not exist, the investigator should use the grade or adjectives: Grade 1 (mild), Grade 2 (moderate), Grade 3 (severe), Grade 4 (life-threatening), or Grade 5 (fatal) to describe the maximum intensity of the adverse event. For purposes of consistency with the CTCAE, these intensity grades are defined in [Table 7-1](#).

Table 7-1. Grading of Adverse Event Severity

Grade	Adjective	Description
Grade 1	Mild	Sign or symptom is present, but it is easily tolerated, is not expected to have a clinically significant effect on the subject's overall health and well-being, does not interfere with the subject's usual function, and is not likely to require medical attention.
Grade 2	Moderate	Sign or symptom causes interference with usual activity or affect clinical status, and may require medical intervention.
Grade 3	Severe	Sign or symptom is incapacitating or significantly affects clinical status and likely requires medical intervention and/or close follow-up.
Grade 4	Life-threatening	Sign or symptom results in a potential threat to life.
Grade 5	Fatal	Sign or symptom results in death.

The distinction between the seriousness and the severity of an adverse event should be noted. Severe is a measure of intensity; thus, a severe reaction is not necessarily a serious reaction. For example, a headache may be severe in intensity, but would not be classified as serious unless it met one of the criteria for serious events listed in [Section 7.1.2](#).

7.3. Evaluation, Intervention, and Drug Discontinuation for Specific Adverse Events or Conditions

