7.3.3. Hepatic Events

Transaminase Elevations: Consistent with observations in a dog toxicology study, reversible asymptomatic ALT/AST increases were also observed early in the idelalisib program in phase 1 studies (101-02 and 101-07) in subjects with hematologic malignancies. Transaminase elevations generally occurred within 4 to 12 weeks of drug initiation, and resolved spontaneously over a period of 2 to 4 weeks with drug being continued for Grade 1 and 2 elevations and drug withheld for Grade 3 or 4 elevations until resolution. These early observations have been consistent with the ongoing experience with idelalisib treatment and transaminase elevations are now well characterized as most frequently asymptomatic, transient and occurring within the first 3 months of treatment.

Grade 1 or 2 elevations commonly resolve despite continued idelalisib treatment and Grade 3 or 4 elevations can be managed by withholding idelalisib. Successful rechallenge after resolution at either the same or lower dose level of idelalisib has been achieved in the majority of subjects. There has been no evidence of impaired synthetic function. Close monitoring of hepatic laboratory tests during therapy is important to allow for appropriate idelalisib interruption and reinstitution so that subjects may continue with study drug treatment.

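### Protocol 6.2.2 places the hepatic draw after Week 16 at Week 168, while Table 6-1 and SAP Appendix 1 place it at Week 24 (Study Day 168); a smaller slip puts Week 8 at Study Day 52

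*Protocol*

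**What the plan says.** On liver tests, Protocol Section 6.2.2 reads: "Blood samples for ALT, AST, total bilirubin will be collected at Screening, Day 1, Weeks 4, 8, 12, 16, 168, every 12 weeks thereafter". An End of Study draw completes the list.

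Table 6-1 of the protocol and Appendix 1 of the SAP mark ALT, AST and total bilirubin at Screening, Week 0, Weeks 4, 8, 12, 16 and 24, and then in the 12-weekly column. In both tables the Week 24 column carries Study Day 168.

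Two other passages describe visit spacing independently of the hepatic row:

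- Section 5.2.5, on dispensing: "idelalisib will be dispensed at 4-week intervals through the first 16 weeks of treatment, at 8-weeks, and at 12-week intervals thereafter".
- Section 6.2.2, on immune monitoring: "Blood samples for immune-monitoring will be collected at Screening, Weeks 4, 12 and every 12 weeks thereafter, and the EOS Visit".

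The pointers to the schedule disagree. The opening of Section 6 names Table 6-1. Section 6.2, which governs visits during treatment, lists "Laboratory lab tests as outlined under section 6.2.2" and then says: "The specific study procedures to be conducted for each subject enrolled in the study are presented in Table 7-1". Section 7.2.2 gives that table's title as "Table 7-1. Grading of Adverse Event Severity".

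Both schedule tables also set Week 8 at Study Day 52 with a window of ±2 days. Footnote b to both tables says: "Absolute neutrophil count (ANC) will be monitored at least every two weeks for the first 24 weeks of idelalisib treatment".

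**The concern.** The number 168 stands in a list of weeks, but in the schedule tables it is a day. A site that follows 6.2.2 as written has no scheduled liver test between Week 16 and Week 168. A site that follows Table 6-1 has one at Week 24 and every 12 weeks after that. No rule says which governs.

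Three things are at stake.

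- **Detection.** Section 7.3.3 states that "transaminase elevations are now well characterized as most frequently asymptomatic, transient and occurring within the first 3 months of treatment". The hepatic actions in Table 5-2 are triggered by the measured grade of ALT, AST or bilirubin. A later, symptom-free elevation has to be measured before any of those actions apply, and without a scheduled draw it may not be. Treatment is open-ended, so subjects can reach the affected weeks.
- **Data.** The laboratory outputs the SAP names are a serum chemistry listing (Section 7.2) and a listing of subjects meeting liver-related criteria (Section 7.2.2). Both depend on these draws.
- **Deviations.** Section 6 requires sites to document departures from protocol procedures, and SAP Section 4.3 lists the important ones. A missed Week 24 draw departs from Table 6-1 but not from 6.2.2.

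The Week 8 entry is a lesser matter. Day 52 breaks the table's own spacing and stretches one neutrophil-count interval beyond the two weeks in footnote b.

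**Working it through.** **Inputs.** Hepatic weeks from Protocol 6.2.2; the hepatic, Week, Study Day and Visit Window rows of Table 6-1 and SAP Appendix 1; dispensing intervals from Protocol 5.2.5; immune-monitoring weeks from 6.2.2.

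**1. Hepatic schedule, side by side**

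| Source | Draws after Day 1 |
|---|---|
| Protocol 6.2.2 | Weeks 4, 8, 12, 16, **168**, then 12-weekly |
| Table 6-1 | Weeks 4, 8, 12, 16, **24**, then 12-weekly |
| SAP Appendix 1 | Weeks 4, 8, 12, 16, **24**, then 12-weekly |

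**2. Where 168 appears in the tables.** 7 × 24 = 168, the Study Day printed over Week 24. As a week, 168 would be Day 7 × 168 = 1176, or 1176/365.25 = 3.2 years. A day number entered among weeks is the likely origin, but the documents do not say so.

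**3. Other passages.** Dispensing is 4-weekly to Week 16, followed by an 8-week step: 16 + 8 = 24. Immune monitoring is at Week 12 and then 12-weekly: 12 + 12 = 24. Both give a Week 24 visit.

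**4. Size of the gap**

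- Literal text: 168 − 16 = 152 weeks; 152 × 7/365.25 = 2.91 years.
- Tables: 24 − 16 = 8 weeks.
- Draws the tables schedule before Week 168 that 6.2.2 omits (Weeks 24, 36, …, 156): (156 − 24)/12 + 1 = 12.

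**5. Week 8 against the grid.** For Weeks 2 to 24 the printed days are 14, 28, 42, 52, 70, 84, 98, 112, 126, 140, 154 and 168. Study Day minus 7 × week is 0 in 11 of the 12 columns, and 52 − 56 = −4 at Week 8. Counting the first dose as Day 1 (7 × week + 1) does not help: the other 11 columns are then off by 1 day and Week 8 by 5.

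- Week 8 window: 52 ± 2 = Days 50 to 54, which excludes Day 56.
- Nominal neutrophil-count intervals: 52 − 42 = 10 days before and 70 − 52 = 18 days after, against 14.
- Longest interval inside the windows: 14 + 4 = 18 days between two on-grid visits, but 18 + 4 = 22 days from Week 8 to Week 10. Day 52 accounts for 4 of those days; the windows already allow the 18.

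**The case against.** The strongest reply is that this is a recognisable slip which the documents largely resolve. Section 6 opens by naming Table 6-1 as the presentation of the procedures. Section 6.3 sends sites to the same table for End of Study laboratory work. Section 9.1.6 ties the case report form to the protocol's schedule of events. A list running 4, 8, 12, 16, 168 looks wrong on sight, and at Week 24 the subject is already on site for dispensing and immune monitoring. The study is also small and descriptive: two centres planned, 3 subjects enrolled, no primary endpoint and no hypothesis test.

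Much of this stands. A careful reader would probably notice the error. The 152-week gap and the 12 omitted draws apply in full only to someone still on treatment at Week 168; the End of Study draw shortens the gap for anyone who stops earlier, and the documents give no expected treatment duration. The SAP does not say whether one missed draw would count as an important deviation. Day 52 is identical in both tables, and because SAP Section 3.8.2 uses the nominal visit, listings by visit do not change.

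The contradiction remains. Section 6.2 is where a site looks during treatment; its laboratory pointer leads to the faulty sentence and its schedule pointer to the wrong table. That a reader can detect the error does not settle which schedule was in force.

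**Conclusion.** The concern holds. Protocol 6.2.2 contradicts Table 6-1 and SAP Appendix 1 on the hepatic draw after Week 16: Week 168 in the text, Week 24 in both tables. On the literal text the gap is at most 152 weeks instead of 8, with up to 12 scheduled draws lost. Those maxima assume that a site follows 6.2.2 as written and that the subject is still on treatment at Week 168.

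The harm is bounded. The Week 4 to 16 draws cover the first 3 months, when Section 7.3.3 says elevations mostly occur, and the End of Study draw and the testing Table 5-2 requires once an elevation is known are untouched. What is exposed is the detection of a later, asymptomatic elevation, and the standard against which a missed draw is judged.

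The Week 8 entry is a genuine but minor inconsistency: 4 days off the grid, affecting scheduling and window deviations only. The point should be corrected; it does not undermine the descriptive analysis.

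**What to change.** - Reconcile Protocol 6.2.2 with Table 6-1 so that the hepatic schedule after Week 16 is stated once and in one unit. Which schedule applies is for the sponsor to confirm.
- In Section 6.2, replace the reference to the severity grading table with one to the schedule table.
- Reconcile the Week 8 Study Day with the grid and with footnote b, in both Table 6-1 and SAP Appendix 1.
- If conduct is complete, add a sentence to the SAP or clinical study report stating which hepatic and Week 8 schedule was followed and used to judge deviations.

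The cost is text only: one schedule entry, one cross-reference and one Study Day in each of two tables, or that single sentence if conduct is complete.
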